7.1.2 Usual resuscitation

For patients randomised to usual resuscitation, all investigations, monitoring and treatment will be instituted, as considered appropriate, by the treating clinician(s). For these patients, the ProMISe early, goal-directed, resuscitation protocol and associated intervention arm equipment will not be provided. As soon as practicable, and according to local practice, patients should be admitted for in-patient care and transferred to an appropriate hospital location.

7.1.3 Co-interventions

All patients may receive additional treatments beyond those prescribed in the resuscitation protocol including antimicrobial agents, steroids and appropriate surgical intervention. All cointerventions will be left to the discretion of the treating clinician(s) and recorded, as per usual practice, in the patient's medical record.

Note that, in keeping with best practice, it is essential that antimicrobial therapy is administered as soon as practicable.

7.2 Management after trial treatment withdrawal

If patients are withdrawn from trial treatment, then they will receive usual resuscitation and care, as per the treating clinician(s) discretion.

8.0 Assessments

Patient details

- Identifiers
- Sociodemographics
- Co-morbidities

Recruitment data

- Date and time of ED presentation
- Inclusion/exclusion criteria
- Date and time met inclusion/exclusion criteria
- Organ dysfunction and illness severity score
- Date and time randomised

Resuscitation data

- Date and time commenced (if randomised to early, goal-directed, protocolised resuscitation arm)
- Line insertion
- Hourly for six hours
 - o Physiological goals
 - o Interventions (amount and type)
- At end of six hours
 - o Organ dysfunction

24 hours from randomisation

- Organ dysfunction
- Interventions (amount and type)

72 hours from randomisation

- Organ dysfunction
- Interventions (amount and type)
- Infection data

Critical care data

Critical care organ support

Hospital data

- Date and time of location change within the hospital
- Date and time of discharge from the hospital
- Discharge location

30 days from randomisation

Safety monitoring data

90 days from randomisation

- Survival status
- Health related Quality of Life (HRQoL)
- Resource use and cost data

1 year from randomisation

- Survival status
- HRQoL
- Resource use and cost data

8.1 Follow-up after initial hospital discharge

All patients surviving to discharge from an acute hospital will be checked against death registrations on the NHS Central Register (NHSCR) for subsequent reporting of mortality data. This will be achieved through regular application of the 'list cleaning' service offered by the Medical Research Information Service (MRIS).

Following randomisation into the trial, the ICNARC CTU will write to each patient's General Practitioner to inform them of the patient's participation in the trial, including a brief description of the trial and a request that the General Practitioner notifies the ICNARC CTU of any events of note.

Patients recorded on the NHSCR as being alive at 90 days and at one year post-randomisation will receive questionnaires to record their health-related quality of life, subsequent hospital admissions and use of personal health services. Questionnaires will be sent with a personally signed letter, a pen enclosed, and a stamped addressed envelope.¹⁸

Health-related quality of life will be measured by the EuroQol (EQ-5D) measure (see: Appendix 3). ¹⁹ EQ-5D is a widely-used generic quality of life measure that can be combined with survival data to calculate Quality-Adjusted Life Years (QALYs). Information on subsequent hospital admissions and the use of personal health services will be recorded on separate healthcare resource use questionnaires. ²⁰

9.0 Data management guidelines

The ProMISe Team, at each site, should attend and document the early, goal-directed, protocolised resuscitation or abstract retrospectively the recorded data, as necessary.

For both arms, organ dysfunction is evaluated by the SOFA score²¹ at baseline, 6 hours and 72 hours, irrespective of location.

All data will be abstracted onto ProMISe paper CRFs. Data are to be entered onto a secure, dedicated, ProMISe web data entry system. The ICNARC CTU will work closely with staff at participating sites to ensure accurate (complete, valid and reliable) data. Extensive completeness, range and consistency checks will further enhance the quality of the data.

Where appropriate, data collection for ProMISe will be piggybacked onto the Case Mix Programme (CMP). Support for the collection and use of patient identifiable data has been approved for the CMP by the Patient Information Advisory Group (PIAG) under Section 251 of the NHS Act 2006 (originally enacted under Section 60 of the Health and Social Care Act 2001) – Approval Number: PIAG 2-10(f)/2005. Section 251 support is reviewed annually by PIAG and covers all aspects of data management including data security. ICNARC is also registered under the Data Protection Act.

9.1 Data collection

All data must be transcribed onto the ProMISe paper CRFs prior to entering onto the secure, dedicated, ProMISe web data entry system. The original ProMISe paper CRFs must be kept at site. All entries must be clear and legible. The use of abbreviations and acronyms must be avoided. The PI is responsible for the accuracy of all data reported in the ProMISe paper CRF. All ProMISe paper CRFs must be completed and signed by staff listed on the ProMISe Trial Delegation Log and authorised by the PI to perform this duty.

Security of the dedicated, ProMISe web data entry system is maintained through user names and frequently updated passwords. Central back-up procedures are in place. Storage and handling of confidential trial data and documents will be in accordance with the Data Protection Act 1998.

9.2 Corrections

Any corrections made to a ProMISe paper CRF at site must be made by drawing a single line through the incorrect item ensuring that the previous entry is not obscured. Each correction must be dated and initialled. Correction fluid must not be used. The amended ProMISe paper CRF must be retained securely at site. These changes must also be made on the secure, dedicated, ProMISe web data entry system.

9.3 Queries

Data entered onto the secure, dedicated, ProMISe web data entry system will be checked centrally at the ICNARC CTU for completeness, accuracy and consistency of data. Queries on incomplete, inaccurate or inconsistent data will be sent to sites. Sites are required to resolve any queries and update the relevant ProMISe paper CRF and data on the secure, dedicated,

ProMISe web data entry system as required. The amended version of the ProMISe paper CRF must be retained at site.

9.4 Timelines for data entry

Web based data entry must be entered at site, from the ProMISe paper CRFs as soon as possible. The ProMISe paper CRFs need to be kept at site for quality assurance, and monitoring purposes in a secure location.

Sites that persistently do not enter data within a timely manner may be suspended from recruiting further patients into the trial by the ICNARC CTU.

10.0 Trial monitoring and oversight

10.1 Monitoring

Sites must agree to allow trial-related monitoring and audits by providing direct access to source data/documents, as required. Patients' informed consent for this will also be obtained.

10.1.1 On-site monitoring

Members of the ICNARC CTU will be carrying out on-site monitoring. Sites will be contacted with details regarding this prior to the on-site monitoring visit.

10.1.2 Monitoring report

Following the monitoring visit, the ICNARC CTU will provide the site with a monitoring report, which will summarise the documents reviewed, along with any findings. The PI at each site will be responsible for ensuring that the findings from the monitoring visit are addressed.

10.1.3 Central monitoring

Data entered onto the secure, dedicated, ProMISe web data entry system will be checked at the ICNARC CTU for completeness, accuracy and consistency of data. Data queries will be issued to the site. Sites are required to resolve any queries and update the relevant ProMISe paper CRF and data on the secure, dedicated, ProMISe web data entry system as required. The amended version must be retained at site. The ICNARC CTU will send reminders for any overdue data or query.

Sites will also be requested to submit ProMISe Screening Logs and ProMISe Trial Delegation Logs to the ICNARC CTU on a regular basis and these will be checked for consistency and completeness.

10.2 Non-compliance

Additional on-site monitoring visits may be scheduled where there is evidence or suspicion of non-compliance by a site to important aspect(s) of the trial requirements.

11.0 Adverse Events

11.1 Definitions of Adverse Events

The following definitions have been adapted from Directive 2001/20/EC and ICH GCP E6:

Adverse Event

Any untoward medical occurrence or effect in a patient treated on a trial protocol, which does not necessarily have a causal relationship with trial treatment. An Adverse Event (AE) can therefore be any unfavourable symptom or disease temporally associated with the use of the trial treatment, whether or not it is related to the trial treatment.

Serious Adverse Event

An AE that:

- results in death;
- is life threatening (the term "life-threatening" refers to an event in which the subject was at risk of death at the time of the event. It does not refer to an event that hypothetically might have caused death if it were more severe);
- requires in-patient hospitalisation or prolongs existing hospitalisation;
- results in persistent or significant disability/incapacity;
- consists of a congenital anomaly or birth defect;
- is otherwise considered to be medically significant by the investigator.

11.2 Recording and Reporting procedures

All patients in ProMISe are critically ill, due to the complexity of the condition, the patients are at increased risk of AEs occurring, many of these events are expected as a result of the patients' medical condition and standard treatment, but may not be related to the trial. Consequently any AEs, not listed in Appendix 4, occurring as a result of the patients' medical condition or standard treatment will not be reported. Pre-existing conditions do not qualify as AEs unless they worsen, these however should be documented in the patient medical notes.

All other AEs that occur between randomisation and 30 days post-the six hours of early, goal-directed, protocolised resuscitation or post-randomisation for those in the usual resuscitation arm must be recorded in the patient medical notes, on the ProMISe paper CRFs and on the secure, dedicated, ProMISe web data entry system. Information regarding date of event onset, severity and relatedness to the trial treatment must be recorded (definitions below). Those meeting the definition of a Serious Adverse Event (SAE) must also be reported to the ICNARC CTU using the trial specific ProMISe SAE Report Form by fax within **24 hours** of observing or learning of the SAE. All sections of the ProMISe SAE Report Form must be completed.

Severity

The site PI or other delegated site investigator(s) must perform an evaluation of severity, for each AE, using the following criteria:

- 1 = Mild
- 2 = Moderate
- 3 = Severe
- 4 = Life-threatening
- 5 = Fatal

Relatedness

The site PI or other delegated site investigator(s) must perform an evaluation of relatedness for each AE. This must be determined as follows:

None

There is no evidence of any causal relationship.

Unlikely

There is little evidence to suggest a causal relationship (e.g. because the event did not occur within a reasonable time after administration of the trial treatment). There is another reasonable explanation of the event (e.g. the patient's clinical condition, other concomitant medications).

Possible

There is some evidence to suggest a causal relationship (e.g. because the event occurs within a reasonable time after administration of the trial procedure). However, the influence of other factors may have contributed to the event (e.g. the patient's clinical condition, other concomitant medications).

Probable

There is evidence to suggest a causal relationship and the influence of other factors is unlikely.

Definitely

There is clear evidence to suggest a causal relationship and other possible contributing factors can be ruled out.

Expectedness

The site PI or other delegated site investigator(s) must perform an evaluation of expectedness for each SAE regardless of causal relationship to the trial procedures. This evaluation must be performed using the list of expected adverse events in Appendix 4. This must be determined as follows:

Expected

The event is listed as an expected AE in Appendix 4 of the ProMISe Protocol.

Unexpected

[figure not shown]
The event is not listed as an expected AE or, the severity of the event is greater than that listed in Appendix 4 of the ProMISe Protocol, for example:

- the event is life threatening or fatal (unless stated in the protocol Appendix 4 as expected).
- the patient presents with an event which is considered to be moderate or severe, but only mild is listed as expected in the ProMISe Protocol Appendix 4.

All SAEs must be reported by faxing a completed SAE Report Form within 24 hours of becoming aware of the event to the ICNARC CTU

[contact]

Adverse Event reporting flowchart

Serious Adverse Event follow-up reports

All SAEs must be followed-up until resolution. The PI or other delegated site investigator(s) must provide follow-up SAE Report(s) if the SAE had not resolved at the time the initial report was submitted.

Serious adverse event processing at the ICNARC CTU

On receipt of the SAE Report, a clinical member of the ICNARC CTU ProMISe Trial Team, on behalf of the Chief Investigator, will evaluate the event for severity, relatedness and expectedness to determine whether or not the case qualifies for expedited reporting. If this is difficult to determine, the Chief Investigator and/or Trial Management Group (TMG) will be consulted for their opinion. In the case of discrepant views, both opinions will be reported.

If the event is evaluated by either the site or a clinical member of the ICNARC CTU ProMISe Trial Team as a related and unexpected SAE, the ICNARC CTU will submit a report to REC within 15 calendar days.

11.3 Clinical review

The ICNARC CTU will provide safety information to the Chief Investigator / TMG / Trial Steering Committee (TSC) / Data Monitoring and Ethics Committee (DMEC) on a periodic basis for review.

11.4 Additional safety monitoring at the ICNARC CTU

The ICNARC CTU will also monitor safety data for any trial related events that are not considered related to the trial treatment. In the event that any trial procedures appear to be resulting in AEs, the Chief Investigator and/or TMG will be contacted for their opinion. If it is declared necessary to review the conduct of the trial, The ICNARC CTU will inform the REC as appropriate.

11.5 Annual progress reports

The ICNARC CTU will submit Annual Progress Reports to the REC. This will commence one year from the date of approval for the trial.

12.0 Withdrawal of patients

In consenting to the trial, patients are consenting to trial treatment, assessments, follow-up and data collection.

12.1 Withdrawal from trial treatment

The treating clinician(s) may withdraw a patient from trial treatment whenever continued participation is no longer in the patient's best interests, but the reasons for doing so must be recorded. In these cases patients remain within the trial for the purposes of follow-up and data analysis according to the treatment arm to which they have been randomised.

If a patient wishes to withdraw from trial treatment, sites should explain the importance of remaining on trial follow-up, or failing this of allowing routine follow-up data to be used for trial purposes and for allowing existing collected data to be used.

12.2 Withdrawal of consent to data collection

If a patient explicitly states their wish not to contribute further data to the trial their decision must be respected and the ICNARC CTU notified in writing. Details should be recorded in the patient's hospital records and no further trial data will be requested.

13.0 Trial closure

13.1 End of trial

The end of the trial will be when the final patient has completed their 1 year follow-up. At which point the Declaration of End of Trial Form will be submitted to the participating ethical committee, as required.

13.2 Archiving of trial documentation

At the end of the trial, the ICNARC CTU will archive securely all centrally held trial related documentation for a minimum of 10 years. Arrangements for its confidential destruction will then be made. It is the responsibility of PIs at each site to keep data and all essential documents relating to the trial held at site for a minimum of 10 years after the end of the trial and in accordance with national legislation and for the maximum period of time permitted by the site, as per local policy.

Essential documents are those which enable both the conduct of the trial and the quality of the data produced to be evaluated and show whether the site complied with the principles of Good Clinical Practice and all applicable regulatory requirements.

If a patient withdraws consent for any data to be used it will be confidentially destroyed.

The ICNARC CTU will notify sites when documentation held at sites may be archived. All archived documents must still be available for inspection and monitoring by appropriate authorities and the the ICNARC CTU upon request.

13.3 Early discontinuation of trial

The trial may be stopped before completion by the Trial Steering Committee (TSC). This can be upon recommendation of the Data Monitoring and Ethics Committee (DMEC). Sites will be informed in writing by the ICNARC CTU of reasons for early closure and the actions to be taken with regard to treatment of patients. Patients should continue to be followed up as per protocol.

13.4 Withdrawal from trial participation by a site

Should a site choose to close to recruitment the PI must inform the ICNARC CTU in writing. Follow up as per protocol must continue for all patients randomised into ProMISe at that site.

Stes that contravene the ProMISe Trial Protocol and the Clinical Trial Site Agreement will be subject to review by the TMG and Sponsor and may be suspended or closed down by the ICNARC CTU.

14.0 Trial management and Trial committees

14.1 Good practice

This trial will be managed according to the Medical Research Council's Guidelines for Good Research Practice, Guidelines for Good Clinical Practice in Clinical Trials and Procedure for Inquiring into Allegations of Scientific Misconduct. The ICNARC CTU has developed its own policies and procedures based on these MRC guidelines, which are adhered to for all research activities at the ICNARC CTU. In addition, the ICNARC CTU has contractual confidentiality agreements with all members of staff. Policies regarding alleged scientific misconduct and breach of confidentiality are reinforced by disciplinary procedures.

14.2 Trial administration

14.2.1 Trial Management Group

All day to day management of ProMISe will be the responsibility of Trial Manager [name] and Chief Investigator, [name]. Staff who work on ProMISe will meet regularly to discuss, the progress of the trial and findings from other related research. The TMG includes the central champions from emergency medicine, acute medicine, and critical care medicine.

14.2.2 Trial Steering Committee

The progress of the trial will be monitored and supervised by the TSC. The TSC will be chaired by [name], Professor of Emergency Medicine, University of Sheffield, as an independent chair. It will also consist of two additional independent members and at least one service user representative.

14.2.3 Data Monitoring and Ethics Committee

The DMEC, will be chaired by [name], Director, Medical Care Research Unit, University of Sheffield, as an experienced statistician and trialist with previous data monitoring committee experience. The DMEC will also include experienced clinicians representing the fields of critical care medicine and emergency medicine. All members of the DMEC will be independent of both the trial and the TSC. The DMEC will operate under the DAMOCLES Charter, ^{40;41} and will report to the TSC, making recommendations on the continuation, or not, of the trial. Safety will be monitored by the DMEC through reporting of SAEs throughout the trial period. The chair of the DMEC will be in contact with their opposite number from the ProCESS and ARISE RCTs to ensure that any important data arising from these studies are made available at the earliest possible opportunity.

14.2.4 Role of the ICNARC CTU

The ICNARC CTU will be responsible for the day to day management and coordination of the trial and will act as custodian of the data. The ICNARC CTU will ensure that all SAEs are appropriately reported to the REC.

15.0 Statistics

15.1 Population for analysis

The target population are adult patients presenting in the ED with early signs of septic shock: systemic inflammatory response, suspected infection and hypotension or hypoperfusion. Subjects will be randomised without regard to race or sex.

15.2 Primary analysis

The primary outcome measure for clinical effectiveness will be 90-day all cause mortality. Patients will be followed to hospital discharge. If discharge from hospital occurs before 90 days, information on subsequent deaths will be obtained through patients' GPs and the NHSCR. The primary outcome measure for cost effectiveness will be the incremental cost per QALY gained at one year.

All analyses will be lodged in a statistical analysis plan, *a priori*, before the investigators are unblinded to any trial outcomes. All analyses will be performed according to the intention to treat principle. Results will be reported in accordance with the CONSORT statement.²⁴ Baseline covariates will be compared between the two arms to observe balance and the success of randomisation. These comparisons will not be subjected to statistical testing, as such tests are invalid.²⁵ The delivery of the protocol will be described in detail.

The primary analysis will test the hypothesis that there is no difference in 90-day mortality for patients randomised to receive early, goal-directed, protocolised resuscitation compared with those randomised to receive usual resuscitation.

The primary analysis will be performed unadjusted using Fisher's exact test. As a supporting analysis, the analysis will be repeated adjusted for baseline covariates using multilevel logistic regression with unit-level random effects. Adjustment for baseline covariates can increase the precision of the estimate of treatment effect, and therefore the power of the trial, and adjust for any bias caused by chance imbalance between the trial arms. The covariates for inclusion in the adjusted analysis will be selected *a priori* based on an established relationship with outcome for patients with severe sepsis and septic shock, and not because of observed imbalance, significance in univariable analyses or by a stepwise selection method.

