2.2.1 Primary objectives

- To estimate the effect of early, goal-directed, protocolised resuscitation compared with usual resuscitation on mortality at 90 days
- To compare incremental cost-effectiveness at one year of early, goal-directed, protocolised resuscitation versus usual resuscitation

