6.1 Randomisation and allocation

A dedicated, 24 hours/seven days per week, telephone randomisation service will be available. In addition, during recruitment, the ProMISe Clinical Advisor, or one of the clinical co-investigators, will be available 24 hours/seven days per week to address any emergency recruitment/randomisation issues.

Randomisation [contact]
Emergency 24/7 [contact]

Allocation to one of the two arms will be by randomised permuted blocks (with variable block lengths of 4, 6 and 8), stratified by recruiting site. As this is a large, multi-centre trial, the risk of chance imbalance in prognostic factors is low and the need to randomise patients during a very short time-window mandates that the randomisation process be as simple as possible. For these reasons, we have elected not to stratify the randomisation process on additional prognostic factors.

Patient randomisation must be performed prior to commencement of any trial intervention.

Following pre-randomisation evaluations (as detailed in Section 5.1), confirmation of eligibility and consent of a patient at a site, the ProMISe Randomisation - Eligibility Form must be fully completed prior to telephoning the randomisation service. The eligibility criteria will be reviewed during the randomisation telephone call. A ProMISe Trial Number and treatment allocation will be assigned, and time of randomisation and date/time of T1 (end of the 'golden' hour) will be stated at the end of the call. These must be recorded at the site by the caller on the ProMISe Randomisation – Eligibility Form.

The telephone randomisation service is provided by Sealed Envelope (http://www.sealedenvelope.com/)

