15.7 Sample size calculation

Estimates for baseline mortality in the usual resuscitation arm have been based on the CMPD. Patients were identified if they were admitted to a critical care unit from the ED having previously been not in hospital and if they satisfied at least two SIRS criteria and had evidence of infection. These definitions are relaxed from the entry criteria to the trial as patients are likely to have had physiological abnormalities stabilised prior to admission to critical care. During 2005 and 2006, 24,155 patients were admitted to 156 participating critical care units

ProMISe v2.3 31/08/2012

from the ED (24 admissions per unit per year). Of these, 6,671 (28%) met the above criteria. Hospital mortality for these patients was 35%. Long-term follow-up studies of patients with severe sepsis indicate that, of patients discharged home from hospital, a further 16% will have died by 90 days.³⁵ However, these studies were predominantly based in the US, where the high provision of chronic care facilities means that more deaths occur outside hospital. We have therefore based our sample size calculations on an anticipated 90-day mortality in the usual resuscitation arm of 40%.

Rivers *et al* reported an absolute risk reduction of 16% in hospital mortality (13% at 60 days);⁴ however, as this was a single-centre trial with concerns over internal and external validity, it is essential that ProMISe is powered to detect a smaller difference.

To achieve 80% power to detect a reduction in 90-day mortality from 40% to 32% associated with early, goal-directed, protocolised resuscitation versus usual resuscitation (P<0.05) requires a sample size of 589 patients per arm (1178 total). Allowing for 6% of patients refusing consent to follow-up (in the similar PAC-Man trial, only 2% of patients refused consent following randomisation) or being lost to follow-up prior to 90 days, we will aim to recruit 630 patients per arm (1260 total). This sample size will give in excess of 99% power to detect an absolute risk reduction of the magnitude observed in the Rivers *et al* trial. In the event that the mortality in the control arm is lower than anticipated, the trial would have greater power to detect the same absolute risk reduction. If the mortality were as low as 25%, the trial would have >80% power to detect a reduction to 18%.

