16.5 Contamination

A theoretical concern in an open trial is that the usual resuscitation arm could gradually incorporate elements of the protocol, thereby affecting the capacity to detect the treatment effect. Contamination will be minimised by:

- the small number of patients recruited from each site;
- frequent ED staff rotation and multiple shifts;
- training, providing the protocol to, and delivering early, goal-directed, protocolised resuscitation by, a locally-determined ProMISe Team;
- delivering usual resuscitation from routine ED staff.

One possible strategy to reduce contamination would be to use a cluster-randomised design. However, heterogeneity, both in terms of standard practice and outcomes, is high and consequently the sample size for a cluster-randomised trial would need to be extremely large to be able to detect the same benefit. Analysis of patients in the CMPD admitted to critical care units from the ED with severe sepsis gives an intraclass correlation coefficient for the between site variation in mortality of 0.04. In the context of this trial, this would translate to a design effect of approximately 2, meaning that around 100 hospitals would need to participate in order to complete the trial in the proposed time frame. We therefore concluded that a cluster-randomised trial would not be feasible. This conclusion is backed up by the experience of a previous large, cluster-randomised trial of a complex critical care intervention delivered outside the critical care unit – the MERIT trial. Despite recruiting over 100,000 patients from 23 hospitals, the between-cluster variation within this trial was higher than anticipated, rendering it underpowered and ultimately inconclusive. In addition to this, outcomes improved over time in the control hospitals suggesting that the cluster-randomised design may not have been effective in reducing contamination.

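### Section 15.2 ranks the planned covariate-adjusted mortality analysis behind an unadjusted Fisher's exact test, and so forgoes additional power that the trial's own data could supply

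*Protocol*

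**What the plan says.** Protocol section 15.2 states: "The primary analysis will be performed unadjusted using Fisher's exact test". As support, "the analysis will be repeated adjusted for baseline covariates using multilevel logistic regression with unit-level random effects". The reason given there for the supporting model is that "Adjustment for baseline covariates can increase the precision of the estimate of treatment effect, and therefore the power of the trial"; it would also deal with chance imbalance. Its covariates are to be fixed in advance for their known link with outcome in sepsis, not picked by observed imbalance, significance or stepwise selection.

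Other sections bear on the choice:

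- Section 6.1: allocation is in permuted blocks, "stratified by recruiting site". Further prognostic factors were left out to keep randomisation quick and simple.
- Sections 8.0 and 9.0: organ dysfunction and an illness severity score are recruitment data, and SOFA is scored at baseline in both arms.
- Section 16.5: a critical care database gives an "intraclass correlation coefficient for the between site variation in mortality of 0.04".
- Section 2.2.1: the first primary objective is "To estimate the effect of early, goal-directed, protocolised resuscitation compared with usual resuscitation on mortality at 90 days". Section 15.2 words the primary analysis as a test of no difference.

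**The concern.** The protocol gives the argument for adjustment and then ranks the adjusted analysis second. It leaves prognostic factors out of the randomisation for practical reasons. That is sound, but it leaves the analysis as the only place where prognosis can be used, and the primary test uses neither prognosis nor site. The trial's main conclusion therefore rests on the least powerful of the mortality analyses it already plans. A true benefit could be missed by the primary test and appear only in the supporting model, where it would carry less weight.

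**Working it through.** **Inputs from the protocol.** 40% against 32% mortality, P<0.05 (taken as two-sided), 80% power, 589 per arm (1178 in all), 6% loss, 630 per arm recruited (section 15.7); at least 48 sites (section 3.1); blocks of 4, 6 and 8 within site (section 6.1); ICC 0.04 (section 16.5). **Assumed:** the prognostic strength of the baseline covariates, AUROC about 0.65 to 0.80.

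**1. The protocol's sample size.** With mean risk 0.36 and difference 0.08:

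n = [1.96 × √(2 × 0.36 × 0.64) + 0.8416 × √(0.40 × 0.60 + 0.32 × 0.68)]² / 0.08² = 563.9, that is 564 per arm.

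With continuity correction:

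n′ = (563.9 / 4) × [1 + √(1 + 4 / (563.9 × 0.08))]² = 588.7, that is 589 per arm.

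The stated 589 is therefore the continuity-corrected figure, which suits Fisher's test; the correction accounts for 589 − 564 = 25 patients per arm. Allowing for loss, 589 / 0.94 = 626.6, consistent with a target of 630.

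**2. Exact power and size, by enumerating all 2×2 tables.**

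- 589 per arm: Fisher 80.0%, uncorrected chi-square 81.6%.
- 630 per arm with no loss: 82.7% and 84.1%.
- Size at 40% in both arms, 589 per arm: Fisher 4.4%, chi-square 5.0%.

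**3. What site and covariates add.** 3000 simulated trials per row, 1178 patients, 48 sites, blocked within site, ICC 0.04, marginal risks 40% and 32%, one normally distributed baseline score. The logistic model contains treatment and the score, without a site term. Monte Carlo standard error is about 0.7 points.

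| AUROC of score (assumed) | Fisher | Chi-square | CMH by site | Logistic + score | Logistic minus Fisher |
|---|---|---|---|---|---|
| no score | 81.0% | 82.0% | 83.0% | – | – |
| 0.66 | 81.6% | 82.7% | 82.9% | 84.6% | 3.0 |
| 0.74 | 81.3% | 82.0% | 82.5% | 87.8% | 6.5 |
| 0.80 | 81.7% | 82.5% | 82.7% | 91.1% | 9.4 |

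Two separate simulations agree:

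- 2500 runs: Fisher 81.2% and 82.2%, CMH 82.5% and 83.4%, adjusted 86.4% and 88.5%, at AUROC 0.68 and 0.74.
- 1500 runs: Fisher 81.7%, adjusted 84.2% at AUROC 0.65 and 88.0% at 0.72.

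CMH gains 1.0 to 2.0 points over Fisher in the table. Over the uncorrected chi-square it gains only 0.2 to 1.0, so much of the step comes from leaving Fisher's conservatism rather than from site itself.

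**4. Type I error of the adjusted test.** Simulated rejection under no effect was 5.0% (3000 runs), and 4.9% and 4.1% (1500 runs). The gain is not bought with false positives.

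**5. Disagreement under a true 8-point benefit (1500 runs).** Adjusted significant and Fisher not: 3.7% of trials at AUROC 0.65 and 7.5% at 0.72. The reverse: 1.2%.

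**6. In patients.** The ratio of (1.96 + z for power)² converts power to sample size. At AUROC 0.68: (1.96 + 1.098)² / (1.96 + 0.885)² = 1.16. At 0.74: (1.96 + 1.200)² / (1.96 + 0.923)² = 1.20. At 0.65: (1.96 + 1.003)² / (1.96 + 0.904)² = 1.07. The gain is worth about 7% more patients at AUROC 0.65 and 15 to 20% at 0.68 to 0.74.

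**The case against.** This is a preference between two valid, pre-specified analyses. Sample size and primary test match, and the promised 80% is delivered. An unadjusted test needs no complete covariates and no model fitted across 48 sites averaging 1260 / 48 ≈ 26 patients, and it tests the marginal difference on which the trial was sized. The site effect is small. The larger gain depends on a covariate strength that the protocol does not state, and the simulated model is simpler than the multilevel one planned. Age, MEDS and SOFA are named in section 15.4 for subgroup interactions, not for adjustment. Swapping the two analyses would not stop them disagreeing.

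All of that stands, and it makes the point an efficiency improvement rather than an error. It does not remove the point: the ranking is fixed in section 15.2 itself, against that section's own argument, and the data needed are already to be collected.

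A reader might infer three stronger things that the protocol does not support:

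- *That ignoring site makes the test invalid or the trial underpowered.* The size stays below 5% and the stated power is met.
- *That the power is given up for nothing.* The unadjusted test buys freedom from model and missing-covariate assumptions.
- *That the primary analysis will yield no effect estimate.* Section 15.2 commits to CONSORT reporting and an analysis plan, and the supporting model gives an adjusted odds ratio. The unadjusted effect measure and its interval are commonly left to that plan, which was not available here.

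**Conclusion.** The point holds as a cheap improvement. Nothing promised is lost. The additional power forgone is about 1 to 2 points from a site-stratified test and about 3 to 9 points from covariate adjustment. The first figure rests on the protocol's ICC of 0.04 and includes the effect of Fisher's conservatism. The second rests on the assumed AUROC of about 0.65 to 0.80 and on one correctly specified, fully observed score. Weaker or incomplete covariates would give less. Where the two analyses disagree under a true benefit, it is more often Fisher's test that misses it.

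**What to change.** Before outcomes are unblinded, reorder the two analyses in section 15.2 and carry the change into the analysis plan.

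- **Primary:** the planned logistic model with site effects and the covariates fixed in advance (for example age and a baseline severity score). The governing estimate is the standardised risk difference with 95% confidence interval, which keeps the result on the absolute scale used for the sample size. The odds ratio is given alongside.
- **Minimum alternative:** a Cochran-Mantel-Haenszel test stratified by site, with the Mantel-Haenszel risk difference and confidence interval. It needs no covariates but gains only about 1 to 2 points.
- **Sensitivity analysis:** the unadjusted Fisher's exact test.
- **Sample size:** unchanged.

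The cost is a short text change, with no new data or patients. The downside is that the primary result then depends on a model, so the covariates and a rule for missing baseline values must be fixed in advance.
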